6.7 Long-term follow-up

No long-term follow-up visits are scheduled or required per study.

With patient consent, date of progression or next CLL therapy will be recorded based on chart review if data are available, or phone call no more than every 6 months.

6.8 Subject Withdrawal or Treatment Discontinuation:

Patients who meet or develop the following criteria should be discontinued from the study

- Active HBV infection or hepatitis. Patients who are carriers of hepatitis B at the time of discontinuation from study treatment will continue to be followed for clinical and laboratory signs of active HBV infection and for signs of hepatitis.
- Severe or life-threatening anaphylaxis or hypersensitivity reaction to rituximab. Patients that discontinue rituximab for that reason can continue to receive HDMP and venetoclax if clinically indicated.
- Patients who meet the following criteria should discontinue HDMP: Grade 4 psychosis; Active HBV infection or hepatitis as above. HDMP doses can be delayed for acute infection or as clinically indicated.
- Inability of patient to comply with study requirements
- Determination by the investigator that it is no longer safe for the patient to continue therapy

With the exception of following HBV, patients who withdraw from all study therapy do not have required follow-up visits and can enter long-term follow-up (6.7). With patient consent, date of progression or next CLL therapy will be recorded.

7.0 Study Medications

7.1 Methylprednisolone Sodium Succinate

7.1.1 Formulation Storage and Preparation

Each vial of methylprednisolone contains 1g of a white powder material. Inactive ingredients include: Benzyl Alcohol, Sodium Hydroxide, Sodium Phosphate, Dibasic Sodium Phosphate and Monobasic Sodium Phosphate. The product is reconstituted in 0.9% saline solution that should be protected from light. Once the product is reconstituted it may be stored at controlled room temperature (68 to 77 degrees F) for use within 48hours.

Methylprednisolone will be prescribed as a standard treatment. Supply: Commercial Supply

7.1.2 Dosage and Administration

Only methylprednisolone sodium succinate should be used for intravenous administration.

HDMP will be administered at 1gr/m2 on Days 1-3 of cycles 0 (with optional repeat for subset of patients who do not greater than low-risk for TLS after 1 cycle). HDMP will be given over 90 minutes and subsequent to the completed infusion, the infusion of Rituximab will be initiated. It will be diluted on 0.9% normal saline and administered directly into a vein over 90 minutes.

7.1.3 Adverse Reactions

Adverse Reactions Significant (Frequency not defined).

Cardiovascular: Arrhythmias, bradycardia, cardiac arrest, cardiomegaly, circulatory collapse, congestive heart failure, edema, fat embolism, hypertension, hypertrophic cardiomyopathy in premature infants, myocardial rupture (post MI), syncope, tachycardia, thromboembolism, vasculitis

Central nervous system: Delirium, depression, emotional instability, euphoria, hallucinations, headache, intracranial pressure increased, insomnia, malaise, mood swings, nervousness, neuritis, personality changes, psychic disorders, pseudotumor cerebri (usually following discontinuation), seizure, vertigo

Dermatologic: Acne, allergic dermatitis, alopecia, dry scaly skin, ecchymoses, edema, erythema, hirsutism, hyper-/hypopigmentation, hypertrichosis, impaired wound healing, petechiae, rash, skin atrophy, sterile abscess, skin test reaction impaired, striae, urticarial

Endocrine & metabolic: Adrenal suppression, amenorrhea, carbohydrate intolerance increased, Cushing's syndrome, diabetes mellitus, fluid retention, glucose intolerance, growth suppression (children), hyperglycemia, hyperlipidemia, hypokalemia, hypokalemic alkalosis, menstrual irregularities, negative nitrogen balance, pituitary-adrenal axis suppression, protein catabolism, sodium and water retention.

Gastrointestinal: Abdominal distention, appetite increased, bowel/bladder dysfunction (after intrathecal administration), gastrointestinal hemorrhage, gastrointestinal perforation, nausea,

pancreatitis, peptic ulcer, perforation of the small and large intestine, ulcerative esophagitis, vomiting, weight gain.

Hematologic: Leukocytosis (transient).

Hepatic: Hepatomegaly, transaminases increased.

Local: Thrombophlebitis.

Neuromuscular & skeletal: Arthralgia, arthropathy, aseptic necrosis (femoral and humoral heads), fractures, muscle mass loss, muscle weakness, myopathy (particularly in conjunction with neuromuscular disease or neuromuscular-blocking agents), neuropathy, osteoporosis, parasthesia, tendon rupture, vertebral compression fractures, weakness.

Ocular: Cataracts, exophthalmoses, glaucoma, intraocular pressure increased.

Renal: Glycosuria.

Respiratory: Pulmonary edema.

Miscellaneous: Abnormal fat disposition, anaphylactoid reaction, anaphylaxis, angioedema, avascular necrosis, diaphoresis, hiccups, hypersensitivity reactions, infections, secondary malignancy, venous thrombosis.

7.1.4 Management of HDMP Induced Hyperglycemia

Subjects that received HDMP frequently present with hyperglycemia. This will be managed following institutional policies including consultation with Endocrinology or Diabetes clinic. A summary of management recommendations is the following:

Subjects will have blood glucose (BG) measured on Days 1-3 of each Cycle during the days of HDMP administration. BG will be measured using a finger stick glucometer after the infusion of HDMP is completed. If a subject has a BG over 201mg/dl, glycemic control will be achieved by giving regular insulin subcutaneously according to the sliding scale below:

BG - 201-250, 4U regular insulin SQ

BG - 251-300, 6U regular insulin SQ

BG - 301-350, 8U regular insulin SQ

BG - 351-400, 10U regular insulin SQ

Those subjects with BG >400 will be managed accordingly to institutional policies and at discretion of the treating physician. Management options will include hypoglycemic agents and insulin. Subjects with BG > 400 will have a fasting BG drawn on Day 3 of Cycle 0 when HDMP is

administered. If this fasting BG is > 200, the subject may be evaluated by an endocrinologist for recommendations regarding their blood sugar management. The same criteria will be applied to any subject with a fasting BG > 200 prior to HDMP administration; this practice will cover those subjects at risk for developing steroid induced diabetes. Long lasting insulin will not be used, nor will the subject be monitored with finger sticks BG during the rest of the treatment cycle unless recommended by Endocrinology-Diabetes clinic.

7.1.5 Dose Adjustment

There are no recommended or planned methylprednisolone dose adjustments. Dosing can be held or stopped for toxicity, as above.

7.2 Rituximab (RITUXAN) – Background information for Rituxan follow in sections 7.2.1 to 7.2.4. However, substitution of rituximab with other equivalent preparations is allowed, including the following: biosimilars of rituximab (including Ruxience or other FDA-approved rituximab product).

7.2.1 Formulation, Storage, and Preparation

RITUXAN vials [100 mg/10 mL single-use vials (NDC 50242-051-21) and 500 mg/50 mL single-use vials (NDC 50242-053-06)] are stable at 2-8C (36F-46F). RITUXAN vials should be protected from direct sunlight. Do not freeze or shake.

Rituxan is prescribed as a standard treatment, Supply: Commercial Supply

7.2.2 Dosage and Administration

Rituximab dosage: Cycle 0 (with HDMP): 100 mg day 1, 375 mg/m2 days 2-4. Cycles 2-6 (with Venetoclax): 500 mg/m2 day 1.

Rituximab is administered as per local clinical standard practices. Specific recommendations are below:

Preparation for Administration: Use appropriate aseptic technique. Withdraw the necessary amount of rituximab and dilute to a final concentration of 1 to 4 mg/mL into an infusion bag containing either 0.9% Sodium Chloride USP or 5% Dextrose in Water USP. Gently invert the bag to mix the solution. Discard any unused portion left in the vial. Parenteral drug products should be inspected visually for particulate matter and discoloration prior to administration. Rituximab solutions for infusion are stable at 2° to 8°C (36° to 46°F) for 24 hours and at room temperature for an additional 12 hours. No incompatibilities between rituximab and polyvinylchloride or polyethylene bags have been observed.

Administration: DO NOT ADMINISTER AS AN INTRAVENOUS PUSH OR BOLUS. Hypersensitivity reactions may occur. Pre-medication, consisting of acetaminophen and diphenhydramine, may be administered before each infusion of rituximab. Pre-medication may attenuate infusion-related events. Since transient hypotension may occur during rituximab

infusion, consideration should be given to withholding anti-hypertensive medications 12 hours prior to rituximab infusion.

Rituximab will be administered as a split dose for the initial rituximab infusion. Routine premedications include diphenhydramine 25-50 mg orally or IV (or other antihistamine), and acetaminophen orally all administered approximately 30 - 60 minutes before the initiation of rituximab infusion. Antiemetics are not routinely administered with rituximab.

Administration of rituximab will be performed in a setting with access to emergency equipment and personnel who are trained to monitor for and respond to medical emergencies. Patients will be monitored during each infusion of study treatment for any adverse effects. Rituximab infusion should be interrupted for severe reactions, and resumed when symptoms have completely resolved. Decrease infusion rate or interrupt infusion if infusion-related events occur. Employ a slower infusion rate (i.e., at least 50% reduction in rate) when therapy is resumed following complete resolution of symptoms.

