7.2.3 Adverse Reactions and Precautions

Infusion Reactions

RITUXAN can cause severe, including fatal, infusion reactions. Severe reactions typically occurred during the first infusion with time to onset of 30-120 minutes. RITUXAN-induced infusion reactions and sequelae include urticaria, hypotension, angioedema, hypoxia, bronchospasm, pulmonary infiltrates, acute respiratory distress syndrome, myocardial infarction, ventricular fibrillation, cardiogenic shock, anaphylactoid events, or death.

Premedicate patients with an antihistamine and acetaminophen prior to dosing. For RA and PV patients, methylprednisolone 100 mg intravenously or its equivalent is recommended 30 minutes prior to each infusion. Institute medical management (e.g. glucocorticoids, epinephrine, bronchodilators, or oxygen) for infusion reactions as needed. Depending on the severity of the infusion reaction and the required interventions, temporarily or permanently discontinue RITUXAN. Resume infusion at a minimum 50% reduction in rate after symptoms have resolved. Closely monitor the following patients: those with pre-existing cardiac or pulmonary conditions, those who experienced prior cardiopulmonary adverse reactions, and those with high numbers of circulating malignant cells (≥25,000/mm³)

Severe Mucocutaneous Reactions

Mucocutaneous reactions, some with fatal outcome, can occur in patients treated with RITUXAN. These reactions include paraneoplastic pemphigus, Stevens-Johnson syndrome, lichenoid dermatitis, vesiculobullous dermatitis, and toxic epidermal necrolysis. The onset of these reactions has been variable and includes reports with onset on the first day of RITUXAN exposure. Discontinue RITUXAN in patients who experience a severe mucocutaneous reaction. The safety of re- administration of RITUXAN to patients with severe mucocutaneous reactions has not been determined.

Hepatitis B Virus (HBV) Reactivation

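### For a severe anaphylactic or hypersensitivity reaction, Section 6.8 discontinues rituximab while Section 7.2.2 interrupts and resumes it after severe reactions, and nothing says which governs

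*Combined protocol and SAP*

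**What the plan says.** **Section 6.8 (Subject Withdrawal or Treatment Discontinuation).** The lead-in is "Patients who meet or develop the following criteria should be discontinued from the study". One criterion is "Severe or life-threatening anaphylaxis or hypersensitivity reaction to rituximab". The same bullet goes on: "Patients that discontinue rituximab for that reason can continue to receive HDMP and venetoclax if clinically indicated". The synopsis repeats this bullet.

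**Section 7.2.2 (rituximab dosage and administration).** The handling text opens with "Rituximab is administered as per local clinical standard practices. Specific recommendations are below". It warns that hypersensitivity can occur, and later says "Rituximab infusion should be interrupted for severe reactions, and resumed when symptoms have completely resolved" and "Employ a slower infusion rate (i.e., at least 50% reduction in rate) when therapy is resumed following complete resolution of symptoms".

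**Section 7.2.3 (Infusion Reactions).** "Depending on the severity of the infusion reaction and the required interventions, temporarily or permanently discontinue RITUXAN". This section counts angioedema, bronchospasm and anaphylactoid events among infusion reactions, and it too describes resumption at a reduced rate.

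**Section 7.2.4.** No rituximab dose adjustments are planned, but doses may be held or skipped for toxicity.

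**Timing.** Cycle 0 rituximab is 100 mg on Day 1 and 375 mg/m2 on each of Days 2, 3 and 4 (Sections 6.2 and 7.2.2, Schedule of Events). Disease burden is reassessed between Day 15 and Day 28 of Cycle 0 (Section 6.2).

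**The concern.** A severe hypersensitivity reaction during an infusion meets the discontinuation criterion in Section 6.8 and also falls within the severe reactions of Section 7.2.2. The first text has rituximab discontinued. The second has the infusion resumed once symptoms resolve. Whether such a patient is re-exposed could then depend on which section the site consults.

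Section 6.8 also conflicts with itself: read literally, its lead-in removes from the study a patient whom the same bullet allows to keep receiving two of the three study drugs.

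There is a smaller statistical consequence. HDMP with rituximab is the debulking treatment under test, and three of its four rituximab doses come after Day 1. Two patients with the same Day 1 reaction could therefore reach the tumor burden reassessment with very different rituximab exposure. Section 9.6 summarizes cycles, modifications and interruptions rather than doses received, so the difference may not be visible beside the debulking result.

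**Working it through.** **1. The plan's own design figures.** Sections 9.2 and 9.7 of the synopsis and Section 9.2 of the main text describe 10 patients in stage 1, stopping at 2 or fewer responses, and rejection at 9 or more of 17. The null rate is 30% and the alternative 60%.

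- P(reject | p) = sum over x = 3 to 10 of P(Bin(10, p) = x) × P(Bin(7, p) ≥ 9 − x).
- p = 0.30: 0.0402 (stated 0.04).
- p = 0.60: 0.8008 (stated 80%).
- Early stopping under the null, P(Bin(10, 0.30) ≤ 2): 0.3828 (stated 38.3%).

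All three reproduce. None of them uses an assumption about how infusion reactions are handled.

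**2. One event under each text.** Take a severe reaction, judged to be hypersensitivity, during the Day 1 infusion.

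| Text | Rituximab | Patient |
|---|---|---|
| 6.8 lead-in | ends with study participation | off study |
| 6.8 bullet, synopsis | discontinued | may continue HDMP and venetoclax |
| 7.2.2 | interrupted, resumed more slowly after full resolution | continues |
| 7.2.3 | temporary or permanent stop, by severity | not stated |
| 7.2.4 | dose held or skipped | not stated |

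The first two rows cannot both be followed as written, and neither agrees with the third. The fourth covers both outcomes but gives no grade at which one becomes the other. Because Section 7.2.3 lists allergic-type events as infusion reactions, a site cannot separate the cases by calling one an infusion reaction and the other hypersensitivity.

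**3. Cycle 0 exposure.** Planned rituximab in one Cycle 0 is 100 + 3 × 375 × BSA = 100 + 1125 × BSA mg. Body surface area (BSA) is not given in the documents; 1.6 to 2.2 m2 is assumed.

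| BSA (m2) | Planned (mg) | Full Day 1 dose only | Half of Day 1 dose |
|---|---|---|---|
| 1.6 | 1900 | 100/1900 = 5.3% | 50/1900 = 2.6% |
| 1.9 | 2237.5 | 100/2237.5 = 4.5% | 50/2237.5 = 2.2% |
| 2.2 | 2575 | 100/2575 = 3.9% | 50/2575 = 1.9% |

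With a wider assumed BSA range of 1.4 to 2.5 m2, the full Day 1 dose is 6.0% to 3.4% of plan. These shares are ceilings for a patient stopped on Day 1, because Section 7.2.3 puts the onset of severe reactions at 30 to 120 minutes and the 100 mg may not all have been infused.

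At the other extreme, a patient who resumes and completes Days 2 to 4 receives up to 100%. Between the two, at 1.9 m2, Days 1 and 2 alone give (100 + 712.5)/2237.5 = 36%, and missing one of the three later doses gives (100 + 1425)/2237.5 = 68%.

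The shares refer to a single Cycle 0. Section 3.0 permits a second cycle only for subjects enrolled before approval of version 5.

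**The case against.** The best defense is that the texts form a hierarchy. Section 7.2 introduces its subsections as background on the product, Section 7.2.2 calls its handling text recommendations under local practice, and Section 6.8 is the trial-specific stopping rule. Section 7.2.3 then bridges them by grading the action on severity. On this view, Section 6.8 names a permanent-stop trigger and Section 7.2 covers the rest. Section 7.2.2 does repeat the trial's rituximab doses, but so do Section 6.2 and the Schedule of Events, so that alone does not make its handling text the governing rule.

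This shows that a tiered reading is plausible. It does not show that the protocol states one: no section gives precedence, and Section 7.2.2 warns of hypersensitivity without exempting it from the resume instruction.

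Other points stand in part. Section 5.2 excludes patients with a history of severe allergic or anaphylactic reactions to monoclonal antibodies, which may make the event less common here. Much of the reporting is already planned: reasons for modifications and interruptions (9.6), subject listings (9.7), and adverse events leading to dose modification or discontinuation (9.8).

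A reader might also infer more than the documents support:

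- **That every severe rituximab reaction is in conflict.** Section 6.8 names only anaphylaxis and hypersensitivity. Other severe infusion reactions fall under Sections 7.2.2 and 7.2.3.
- **That the patient receives either 4% to 5% or everything.** Those are the extremes. Sections 7.2.3 and 7.2.4 allow amounts between them, and resuming one infusion does not ensure that Days 2 to 4 are given.
- **That Day 1 is the first rituximab exposure.** It is the first on-study dose. Section 5.1 requires prior therapy and allows prior HDMP with rituximab, so the remark in Section 7.2.3 about first infusions may not apply to every patient.
- **That one such patient can decide the trial at 9 of 17.** That is true of any patient for any reason and does not measure this problem.

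**Conclusion.** The inconsistency is real and should be corrected. A severe anaphylactic or hypersensitivity reaction to rituximab meets incompatible instructions in Sections 6.8 and 7.2.2, Section 7.2.3 does not settle them, and the lead-in to Section 6.8 conflicts with its own bullet. Its main weight is patient safety, because re-exposure after such a reaction is left undetermined.

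The statistical consequence is secondary. Rituximab received before the Day 15 to 28 reassessment can range from at most about 4% to 5% of plan (stopped on Day 1, assumed BSA 1.6 to 2.2 m2) up to 100%, with intermediate amounts possible.

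This does not translate into an effect on the primary endpoint. The documents give neither the frequency of these reactions in this trial nor the debulking probability after truncated rituximab. Failure to debulk cannot be assumed either: HDMP may continue, and Section 2.3 reports partial responses to HDMP alone in 6 of 11 patients, though after four cycles on average and on a five-day schedule. The stated type I error, power and early stopping probability are unaffected. No view is taken here on which clinical rule is right.

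**What to change.** Reconcile Section 6.8 (lead-in and bullet), the matching synopsis text, and Sections 7.2.2 and 7.2.3 so that each type and grade of rituximab reaction leads to one action. State whether that action applies to the current infusion, to all further rituximab, or to study participation. State which section governs if any wording is left to local practice. The clinical team decides the content. The cost is amendment wording.

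Optionally, add to the Section 9.6 exposure summary a listing of patients who did not receive all four Cycle 0 rituximab doses, with the reason and the debulking result. The cost is one listing. It matters because Section 9.6 does not define what counts as a cycle received, so a patient given only the Day 1 dose could otherwise be counted as having had one.

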7.2.3 Adverse Reactions and Precautions

Infusion Reactions

RITUXAN can cause severe, including fatal, infusion reactions. Severe reactions typically occurred during the first infusion with time to onset of 30-120 minutes. RITUXAN-induced infusion reactions and sequelae include urticaria, hypotension, angioedema, hypoxia, bronchospasm, pulmonary infiltrates, acute respiratory distress syndrome, myocardial infarction, ventricular fibrillation, cardiogenic shock, anaphylactoid events, or death.

Premedicate patients with an antihistamine and acetaminophen prior to dosing. For RA and PV patients, methylprednisolone 100 mg intravenously or its equivalent is recommended 30 minutes prior to each infusion. Institute medical management (e.g. glucocorticoids, epinephrine, bronchodilators, or oxygen) for infusion reactions as needed. Depending on the severity of the infusion reaction and the required interventions, temporarily or permanently discontinue RITUXAN. Resume infusion at a minimum 50% reduction in rate after symptoms have resolved. Closely monitor the following patients: those with pre-existing cardiac or pulmonary conditions, those who experienced prior cardiopulmonary adverse reactions, and those with high numbers of circulating malignant cells (≥25,000/mm³)

Severe Mucocutaneous Reactions

Mucocutaneous reactions, some with fatal outcome, can occur in patients treated with RITUXAN. These reactions include paraneoplastic pemphigus, Stevens-Johnson syndrome, lichenoid dermatitis, vesiculobullous dermatitis, and toxic epidermal necrolysis. The onset of these reactions has been variable and includes reports with onset on the first day of RITUXAN exposure. Discontinue RITUXAN in patients who experience a severe mucocutaneous reaction. The safety of re- administration of RITUXAN to patients with severe mucocutaneous reactions has not been determined.

Hepatitis B Virus (HBV) Reactivation

Hepatitis B virus (HBV) reactivation, in some cases resulting in fulminant hepatitis, hepatic failure and death, can occur in patients treated with drugs classified as CD20-directed cytolytic antibodies, including RITUXAN. Cases have been reported in patients who are hepatitis B surface antigen (HBsAg) positive and also in patients who are HBsAg negative but are hepatitis B core antibody (anti-HBc) positive. Reactivation also has occurred in patients who appear to have resolved hepatitis B infection (i.e., HBsAg negative, anti-HBc positive and hepatitis B surface antibody [anti-HBs] positive).

HBV reactivation is defined as an abrupt increase in HBV replication manifesting as a rapid increase in serum HBV DNA levels or detection of HBsAg in a person who was previously HBsAg negative and anti-HBc positive. Reactivation of HBV replication is often followed by hepatitis, i.e., increase in transaminase levels. In severe cases increase in bilirubin levels, liver failure, and death can occur.

Screen all patients for HBV infection by measuring HBsAg and anti-HBc before initiating treatment with RITUXAN. For patients who show evidence of prior hepatitis B infection (HBsAg positive [regardless of antibody status] or HBsAg negative but anti-HBc positive), consult with physicians with expertise in managing hepatitis B regarding monitoring and consideration for HBV antiviral therapy before and/or during RITUXAN treatment.

Monitor patients with evidence of current or prior HBV infection for clinical and laboratory signs of hepatitis or HBV reactivation during and for several months following RITUXAN therapy. HBV reactivation has been reported up to 24 months following completion of RITUXAN therapy.

In patients who develop reactivation of HBV while on RITUXAN, immediately discontinue RITUXAN and any concomitant chemotherapy, and institute appropriate treatment. Insufficient data exist regarding the safety of resuming RITUXAN treatment in patients who develop HBV reactivation. Resumption of RITUXAN treatment in patients whose HBV reactivation resolves should be discussed with physicians with expertise in managing HBV.

Progressive Multifocal Leukoencephalopathy (PML)

JC virus infection resulting in PML and death can occur in RITUXAN-treated patients with hematologic malignancies or with autoimmune diseases. The majority of patients with hematologic malignancies diagnosed with PML received RITUXAN in combination with chemotherapy or as part of a hematopoietic stem cell transplant. The patients with autoimmune diseases had prior or concurrent immunosuppressive therapy. Most cases of PML were diagnosed within 12 months of their last infusion of RITUXAN.

Consider the diagnosis of PML in any patient presenting with new-onset neurologic manifestations. Evaluation of PML includes, but is not limited to, consultation with a neurologist, brain MRI, and lumbar puncture.

Discontinue RITUXAN and consider discontinuation or reduction of any concomitant chemotherapy or immunosuppressive therapy in patients who develop PML.

Tumor Lysis Syndrome (TLS)

Acute renal failure, hyperkalemia, hypocalcemia, hyperuricemia, or hyperphosphatemia from tumor lysis, sometimes fatal, can occur within 12-24 hours after the first infusion of RITUXAN in patients with NHL. A high number of circulating malignant cells (>25,000/mm³) or high tumor burden, confers a greater risk of TLS.

Administer aggressive intravenous hydration and anti-hyperuricemic therapy in patients at high risk for TLS. Correct electrolyte abnormalities, monitor renal function and fluid balance, and administer supportive care, including dialysis as indicated.

Infections

Serious, including fatal, bacterial, fungal, and new or reactivated viral infections can occur during and following the completion of RITUXAN-based therapy. Infections have been reported in some patients with prolonged hypogammaglobulinemia (defined as hypogammaglobulinemia >11 months after rituximab exposure). New or reactivated viral infections included cytomegalovirus, herpes simplex virus, parvovirus B19, varicella zoster virus, West Nile virus, and hepatitis B and C. Discontinue RITUXAN for serious infections and institute appropriate anti-infective therapy. RITUXAN is not recommended for use in patients with severe, active infections.

Cardiovascular Adverse Reactions

Cardiac adverse reactions, including ventricular fibrillation, myocardial infarction, and cardiogenic shock may occur in patients receiving RITUXAN. Discontinue infusions for serious or life-threatening cardiac arrhythmias. Perform cardiac monitoring during and after all infusions of RITUXAN for patients who develop clinically significant arrhythmias, or who have a history of arrhythmia or angina.

Renal Toxicity

Severe, including fatal, renal toxicity can occur after RITUXAN administration in patients with NHL. Renal toxicity has occurred in patients who experience tumor lysis syndrome and in patients with NHL administered concomitant cisplatin therapy during clinical trials. The combination of cisplatin and RITUXAN is not an approved treatment regimen. Monitor closely for signs of renal failure and discontinue RITUXAN in patients with a rising serum creatinine or oliguria.

Bowel Obstruction and Perforation

Abdominal pain, bowel obstruction and perforation, in some cases leading to death, can occur in patients receiving RITUXAN in combination with chemotherapy. In postmarketing reports, the mean time to documented gastrointestinal perforation was 6 (range 1-77) days in patients with NHL. Evaluate if symptoms of obstruction such as abdominal pain or repeated vomiting occur.

Immunization

The safety of immunization with live viral vaccines following RITUXAN therapy has not been studied and vaccination with live virus vaccines is not recommended before or during treatment.

For RA patients, physicians should follow current immunization guidelines and administer non-live vaccines at least 4 weeks prior to a course of RITUXAN.

The effect of RITUXAN on immune responses was assessed in a randomized, controlled study in patients with RA treated with RITUXAN and methotrexate (MTX) compared to patients treated with MTX alone.

A response to pneumococcal vaccination (a T-cell independent antigen) as measured by an increase in antibody titers to at least 6 of 12 serotypes was lower in patients treated with RITUXAN plus MTX as compared to patients treated with MTX alone (19% vs. 61%). A lower proportion of patients in the RITUXAN plus MTX group developed detectable levels of anti-keyhole limpet hemocyanin antibodies (a novel protein antigen) after vaccination compared to patients on MTX alone (47% vs. 93%).

A positive response to tetanus toxoid vaccine (a T-cell dependent antigen with existing immunity) was similar in patients treated with RITUXAN plus MTX compared to patients on MTX alone (39% vs. 42%). The proportion of patients maintaining a positive Candida skin test (to evaluate delayed type hypersensitivity) was also similar (77% of patients on RITUXAN plus MTX vs. 70% of patients on MTX alone).

Most patients in the RITUXAN-treated group had B-cell counts below the lower limit of normal at the time of immunization. The clinical implications of these findings are not known.

Embryo-Fetal Toxicity

Based on human data, RITUXAN can cause fetal harm due to B-cell lymphocytopenia in infants exposed to rituximab in-utero. Advise pregnant women of the risk to a fetus. Females of childbearing potential should use effective contraception while receiving RITUXAN and for 12 months following the last dose of RITUXAN.

